Official title: Evaluation of the clinical and molecular efficacy of daily avanafil in Egyptian males with erectile and endothelial dysfunction (Randomized Placebo-Controlled study)

NCT number: NCT04374994

Document date: 20-9-2018

Statistical analysis of the data: Data were fed to the computer and analyzed using IBM SPSS software package version 20.0. Qualitative data were described using number and percent. Quantitative data were described using range (minimum and maximum), mean, standard deviation and median. Significance of the obtained results was judged at the 5% level. Student t-test was used for normally distributed quantitative variables, to compare between two studied groups. Mann Whitney test for abnormally distributed quantitative variables, to compare between two studied groups. Wilcoxon signed ranks test, for abnormally distributed quantitative variables, to compare between two periods. Paired t-test for normally quantitative variables, to compare between two periods Spearman coefficient for correlation between two abnormally quantitative variables.

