Recently, a new PDE5i, avanafil, has become available worldwide. The evaluation of safety profile suggests that avanafil is associated with a lower incidence of side effects and approved for the treatment of ED by both the US Food and Drug Administration (FDA) and the European Medicines Agency (EMA) in April 2012 and in June 2013, respectively. ⁽¹³⁻¹⁵⁾

The most important characteristic of avanafil, in comparison to the first-generation PDE5is, is its high selectivity for PDE5, particularly in relation to PDE6, PDE1, and PDE11. Avanafil has selectivity for PDE5 over PDE1 and PDE6 similar to tadalafil, but, unlike tadalafil, has negligible affinity for PDE11. ^(14,15)

AIM OF THE WORK

The aim of the work is to investigate the impact of daily avanafil on the function and levels of some soluble molecular markers of penile endothelium in men with erectile dysfunction.

PATIENTS

The study will be conducted on 140 adult males complaining of ED associated with diseases that may affect endothelial function such as diabetes mellitus, hypertension and/or dyslipidemia from outpatient clinic of Dermatology, Venereology and Andrology Department of the Alexandria main University Hospital.

They will be randomized into two groups:

Intervention group: will include seventy adult males and will receive daily avanafil for four weeks.

Control group: will include seventy adult males and will receive a placebo instead.

- An informed consent will be taken from all subjects prior to the onset of the study.
- Approval of the medical ethics committee of Alexandria Faculty of Medicine will be obtained.

Exclusion criteria:

1. Patients aged < 18 years.
2. Patients with contraindications to treatment by PDE inhibitors.
3. Patients with diseases that increase the risk of priapism (eg, leukemia and multiple myeloma).

METHODS

ALL studied groups will be subjected to:

1. Full history taking with complete general and genital examination.
2. Diagnosis and severity of ED was determined according to IIEF-5 questionnaire. Erectile dysfunction will be defined as a score of < 22 in the self reported International Index of Erectile Function-5 questionnaire (IIEF-5).⁽¹⁶⁾

The International Index of Erectile Function (IIEF-5) Questionnaire

Over the past 6 months:					
1. How do you rate your confidence that you could get and keep an erection?	Very low 1	Low 2	Moderate 3	High 4	Very high 5

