2. When you had erections with sexual stimulation, how often were your erections hard enough for penetration?	Almost never/never 1	A few times (much less than half the time) 2	Sometimes (about half the time) 3	Most times (much more than half the time) 4	Almost always/always 5
3. During sexual intercourse, how often were you able	Almost never/never 1	A few times (much	Sometimes (about half the time) 3	Most times (much	Almost always/always 5

The International Index of Erectile Function (IIEF-5) Questionnaire

to maintain your erection after you had penetrated (entered) your partner?		less than half the time) 2		more than half the time)4	
4. During sexual intercourse, how difficult was it to maintain your erection to completion of intercourse?	Extremely difficult 1	Very difficult 2	Difficult 3	Slightly difficult 4	Not difficult 5
5. When you attempted sexual intercourse, how often was it satisfactory for you?	Almost never/never 1	A few times (much less than half the time) 2	Sometimes (about half the time) 3	Most times (much more than half the time) 4	Almost always/always 5

IIEF-5 scoring:

The IIEF-5 score is the sum of the ordinal responses to the 5 items.

22-25: No erectile dysfunction

17-21: Mild erectile dysfunction

The International Index of Erectile Function (IIEF-5) Questionnaire

12-16: Mild to moderate erectile dysfunction

8-11: Moderate erectile dysfunction

5-7: Severe erectile dysfunction

3. The patients in the intervention group will receive avanafil 50 mg orally for 4 weeks. They will be instructed to take their medication on an empty stomach every evening. A total of 28 pills will be prescribed at study entry and patients will be asked to count and report any unused medication at the end-of-study visit.
4. The patients in the control group will receive placebo tablets for 4 weeks.
5. Markers of endothelial function will be measured in plasma at baseline and end of treatment using standard methods and commercially available kits (Human Endothelin 1(ET-1) ELISA Kit, Nitric oxide (NO) ELISA Kit and Human Cyclic guanosine monophosphate(cGMP) ELISA Kit).⁽¹⁷⁻¹⁹⁾
6. The primary outcome will be the percentage of change of NO, cGMP and ET1 serum levels from baseline to 4 weeks posttreatment with avanafil.
7. The secondary outcome will be comparing avanafil with placebo group regarding posttreatment NO, cGMP and ET1 serum levels and percentage of change from baseline.

ETHICS OF RESEARCH

Research on human or human products:

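### Three markers are jointly primary with no written success rule and a flat 5% level; if any one marker suffices, family-wise error is 14.3% for independent markers (at most 15.0%)

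*SAP*

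**What the plan says.** Protocol, METHODS, item 6: "The primary outcome will be the percentage of change of NO, cGMP and ET1 serum levels from baseline to 4 weeks posttreatment with avanafil". Three markers share one primary outcome. None is ranked first and they are not combined into a composite.

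Protocol, METHODS, item 7: "The secondary outcome will be comparing avanafil with placebo group regarding posttreatment NO, cGMP and ET1 serum levels and percentage of change from baseline". The randomized comparison is thus secondary, although the PATIENTS section sets up a concurrent control: "Control group: will include seventy adult males and will receive a placebo instead".

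SAP, Statistical analysis of the data: "Significance of the obtained results was judged at the 5% level". This is the only statement on error rates in either document. The SAP lists tests by type of data, for example "Student t-test was used for normally distributed quantitative variables, to compare between two studied groups" and "Wilcoxon signed ranks test, for abnormally distributed quantitative variables, to compare between two periods", but assigns none of them to an outcome. Neither document gives a success rule, an alpha split, a testing order or the sidedness of the tests.

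**The concern.** With three primary markers, each judged at 5%, the error rate of the primary conclusion depends on how the three results are combined. That rule is not written. If any one marker suffices, the plan gives three chances of a false positive and the rate exceeds 5%. If all three are required, it does not. A rule chosen after the p-values are known could not be defended.

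Which tests form the family also matters. Item 6 is worded as change under avanafil. An adjustment applied to three within-arm tests would control error only for the hypothesis of no change over 4 weeks. It would not protect a claim of drug effect, because any change unrelated to the drug, such as regression to the mean or a time trend, also makes that hypothesis false.

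**Working it through.** **Inputs from the documents.** Three primary markers (protocol, item 6); 5% for each result (SAP); 140 men, 70 per arm (protocol, PATIENTS). The documents state no family-wise rate, effect size, SD or power, so there is no figure of the plan's own to reproduce beyond the 5%.

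**Assumptions.** Two-sided tests, normal data, equal pairwise correlation ρ between the markers' test statistics, no dropout. The documents give no correlation, so a range is shown.

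**1. Any one marker suffices, each tested at 5%, no effect on any marker.**
- Independent markers: 1 − (1 − 0.05)³ = 1 − 0.857375 = 0.1426, or 14.3%.
- Any dependence (Bonferroni bound): 3 × 0.05 = 0.15, or 15.0%.
- Correlated markers: integration over an equicorrelated normal distribution, two-sided 5% each (middle column below).

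**2. The same with Holm.** When no marker has an effect, a family-wise error occurs exactly when the smallest p-value falls below 0.05/3 = 0.0167. For independent markers this is 1 − (1 − 0.0167)³ = 0.049.

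| ρ | Any one at 5% | Holm |
|---|---|---|
| 0 | 14.3% | 4.9% |
| 0.3 | 13.6% | 4.8% |
| 0.5 | 12.5% | 4.5% |
| 0.7 | 10.9% | 3.9% |
| 0.9 | 8.4% | 3.0% |

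**3. All three required at 5%.** A false claim needs every test to reject, including the test of a marker with no effect, so the rate cannot exceed 5%.

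**4. Why the family should be between-arm.** Assume no drug effect but a non-drug shift of 0.2 SD of the change score. A paired t-test with n = 70 then rejects with probability 0.378 at 5% and 0.225 at 0.0167.
- At least one of three independent markers, unadjusted: 1 − (1 − 0.378)³ = 0.76.
- Under Holm: 1 − (1 − 0.225)³ = 0.53.
- At ρ = 0.5 (simulation): 63% and 43%.
- With a milder assumed shift of 0.1 SD, independent markers, Holm: 16.5%.
- The same shift in both arms cancels in the between-arm tests, so their Holm error stays at 4.9% (ρ = 0) and 4.5% (ρ = 0.5).

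**5. Power cost of Holm between arms** (two-sample t-test, noncentral t, 70 per arm). The effect detectable with 80% power is 0.477 SD at 5%, 0.526 SD at 2.5% and 0.553 SD at 1.67%. At 0.477 SD, power at the strictest step falls from 80% to 65%; 94 per arm would restore it (80.2%).

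If all three markers truly differ by 0.477 SD (simulation):

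| Result | ρ = 0 | ρ = 0.5 |
|---|---|---|
| At least one marker passes Holm | 96% | 87% |
| A given marker passes Holm | 75% | 73% |
| All three significant at 5% | 51% | 61% |

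For comparison, the within-arm paired test with n = 70 detects 0.340 SD at 5% with 80% power.

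**The case against.** The strongest reply is that 14.3% belongs to a rule no document contains. Item 6 lists the markers together and never says that one is enough. If all three were meant, there is no inflation, and if the markers are strongly correlated, the any-one rate is well below 14.3%. This stands as a limit on the number: what the documents support is a range from at most 5% to at most 15%, depending on the missing rule. It does not answer the omission, since even at a correlation of 0.9 the any-one rate is 8.4%.

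A second reply is that confirmatory testing is not established. Item 6 names an outcome and no test, the stated aim is investigative, and there is no hypothesis or power target. That has some force, and an exploratory label would be a sufficient remedy. But the documents do not use that label. The title speaks of efficacy in a randomized placebo-controlled study, and the SAP judges its results for significance.

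A third reply is that a within-arm primary outcome is a different problem from multiplicity. This is fair as to size: the 76% and 53% figures come mainly from the assumed shift, since a single within-arm test would already reject in 38% of trials. They do not measure the multiplicity. They show why the adjustment must be attached to the between-arm tests if it is to protect a claim about the drug.

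**Conclusion.** The concern holds. The plan has three co-primary markers, a flat 5% level and no rule for combining them, so the error rate of its primary conclusion is not fixed. Under an any-one reading it is 14.3% for independent markers, falls with positive correlation, and is at most 15.0%. Under an all-three reading it is at most 5%. The independent-marker figure and the ceiling require only that each test has size 5%; the figures for correlated markers also assume two-sided tests and equal correlations. The within-arm figures rest on an assumed shift and bear on the choice of family only. This should be fixed: it affects the primary conclusion, and the remedy is short.

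**What to change.** Before results are seen, amend protocol items 6 and 7 so that the avanafil-versus-placebo comparison of percentage change is primary, and add to the SAP:

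> The primary family is three tests, one per marker (NO, cGMP, ET-1), each comparing avanafil with placebo on percentage change from baseline to week 4, by a two-sided Student t-test, or by Mann-Whitney where that was fixed for the marker before any comparison by arm. The primary result is positive if at least one marker passes Holm: smallest p against 0.0167, next 0.025, last 0.05, stopping at the first failure. Claims are limited to markers that pass. All other tests are secondary or exploratory.

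Equally acceptable, if written in advance: all three markers required at 5%, a fixed testing order, or one lead marker. If item 6 stays within-arm, state that Holm then controls error only for no change over 4 weeks and supports no claim of drug effect. If no confirmatory claim is intended, label all three marker results exploratory; no adjustment is then needed.

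The SAP is written in the past tense ("Data were fed to the computer and analyzed using IBM SPSS software package version 20.0"). The sponsor should confirm that the rule is fixed before the data are analysed; otherwise the marker results should be reported as exploratory.

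The cost is one SAP paragraph and an amendment to two protocol items. No new measurement is needed, because item 7 already compares percentage change and the SAP already lists the between-group tests. The price is sensitivity: the detectable effect rises from 0.34 SD (within-arm) to 0.48 SD (between-arm) at 5%, and to 0.55 SD at Holm's strictest step.

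### The SAP names no test or single summary for the primary outcome, within-arm percentage change; if the mean of individual percentage changes is reported, it is biased upward under no effect

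*SAP*

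**What the plan says.** Protocol, METHODS, item 6: "The primary outcome will be the percentage of change of NO, cGMP and ET1 serum levels from baseline to 4 weeks posttreatment with avanafil". The comparison with placebo comes separately in item 7: "The secondary outcome will be comparing avanafil with placebo group regarding posttreatment NO, cGMP and ET1 serum levels and percentage of change from baseline".

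The SAP is one paragraph. For within-arm comparisons it gives "Paired t-test for normally quantitative variables, to compare between two periods" and "Wilcoxon signed ranks test, for abnormally distributed quantitative variables, to compare between two periods". For between-arm comparisons it gives "Student t-test was used for normally distributed quantitative variables, to compare between two studied groups" and "Mann Whitney test for abnormally distributed quantitative variables, to compare between two studied groups". The summaries are generic: "Quantitative data were described using range (minimum and maximum), mean, standard deviation and median". So is the error level: "Significance of the obtained results was judged at the 5% level".

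The SAP does not attach any of these tests to a named variable. It does not say how percentage change is calculated or which summary represents it, and it mentions no log or ratio scale.

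**The concern.** A two-period test needs two values per patient. Percentage change is already one value per patient. The two-period tests therefore fit the baseline and week-4 levels, and nothing on the list tests a within-arm percentage change. Differences in level are driven by patients with high values, and percentage changes by patients with low baselines, so the two can point in different directions for the same marker.

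The open choice of summary matters as well. Percentage change is asymmetric: a patient who goes from 100 to 150 scores +50%, one who goes from 150 to 100 scores −33.3%, and the average is (50 − 33.3)/2 = +8.3% although nothing has changed overall. A rise is the hoped-for result for NO and cGMP, so the artefact helps avanafil there. A fall is hoped for in ET-1, and there the artefact works against the drug. The error falls on the estimate that the protocol calls primary.

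**Working it through.** **Inputs.** From the documents: 70 patients per arm (Protocol, PATIENTS), one baseline and one end-of-treatment value per marker (METHODS, item 5), and the 5% level, taken as two-sided because the SAP does not say. Assumed, because the documents give no variability for any marker: log-normal levels, log-scale SD s = 0.3, 0.5 or 0.7, and baseline to week-4 correlation r = 0.5 or 0.9. The plan states no figure of its own on this point to reproduce.

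**Step 1: direction.** Let X be baseline and Y week 4, positive and exchangeable (no drug or time effect). Then E[Y/X] = E[(Y/X + X/Y)/2] ≥ 1, with equality only if Y = X. The mean percentage change is positive under no effect whatever the distribution.

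**Step 2: size.** In the log-normal case log(Y/X) has mean 0 and variance 2s²(1−r), so the expected mean percentage change is exp(s²(1−r)) − 1. This equals the squared within-patient coefficient of variation (CV).

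| s | r = 0.9 | r = 0.5 |
|---|---|---|
| 0.3 | exp(0.009) − 1 = +0.9% | exp(0.045) − 1 = +4.6% |
| 0.5 | exp(0.025) − 1 = +2.5% | exp(0.125) − 1 = +13.3% |
| 0.7 | exp(0.049) − 1 = +5.0% | exp(0.245) − 1 = +27.8% |

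By within-patient CV, the bias is +0.25% at 5%, +1% at 10%, +4% at 20% and +9% at 30%.

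**Step 3: ET-1.** Take a true geometric fall of 10% and r = 0.5. The expected mean percentage change is 0.9 × 1.046 − 1 = −5.9% at s = 0.3, and 0.9 × 1.133 − 1 = +2.0% at s = 0.5. The sign can reverse.

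**Step 4: other summaries and tests, simulated under no effect with n = 70** (within-patient CV 5% to 50%).
- Median percentage change: averages 0.0% to 0.5%.
- Paired t-test on levels: rejects in 4.5% to 5.0% of trials.
- Wilcoxon test on levels: 4.5% to 5.9%.
- One-sample t-test on the log ratio: 4.7% to 5.2%.
- Two-arm t-test on percentage change: 4.5% to 5.1%, because both arms carry the same bias.

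**Step 5: between-arm efficiency.** On the log scale, an unadjusted change has variance proportional to 2(1−r), and an analysis adjusted for baseline (ANCOVA) has variance proportional to 1 − r². The relative efficiency is (1 + r)/2: 0.75 at r = 0.5 and 0.85 at r = 0.7. Set the effect so that ANCOVA has nominal 80% power (1.96 + 0.84 = 2.80 standard errors). The unadjusted log ratio then has power Φ(2.80√0.75 − 1.96) = 68% and Φ(2.80√0.85 − 1.96) = 73%. In simulation with 70 per arm, percentage change analysed by t-test or Mann-Whitney according to a Shapiro-Wilk check had about 65% to 70% power where log-scale ANCOVA had 76% to 79%. Most of the gap comes from not adjusting for baseline. The percentage scale and the normality switch cost only about 1 to 3 points.

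**The case against.** A reader might infer that the SAP's own tests will produce false positive findings. They will not: the paired t-test and the Wilcoxon test, applied to levels, keep about 5% error. That they are applied to levels is itself an inference, though the natural one, since the SAP names no variable.

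A reader might also test the mean percentage change against zero with a one-sample t-test. At r = 0.5 that would reject in about 19%, 42% and 66% of null trials for s = 0.3, 0.5 and 0.7. Those rates cannot be charged to this plan, because the SAP contains no such test. Under this model percentage change would rarely pass a normality check, and a signed-rank test on it would reject in about 8%, 14% and 22%: inflated, but much less.

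Three further points stand. The SAP lists the median, which nearly removes the bias. The documents do not say whether percentage change means the average of individual changes or the change in a group mean or median, and the bias belongs to the mean of individual changes. The size also depends on variability that the documents do not give; at a within-patient CV of 5% it is negligible.

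Finally, the comparison with placebo is not biased under no effect. That is true, but METHODS item 7 makes it secondary, so it does not repair the within-arm primary result.

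These points limit the concern without removing it. The plan still leaves the calculation, summary and test of its primary outcome open, and one summary it permits is biased.

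**Conclusion.** The concern holds in a limited form, and the SAP should be changed. The primary outcome has no named test and no single summary, and the p-value most likely to accompany it is on another scale. If the mean of individual percentage changes is reported, it overstates change under no effect by about +1% to +5% at r = 0.9 and +5% to +28% at r = 0.5, for s from 0.3 to 0.7. The direction follows from exchangeability alone. The size rests on the assumed s, r and log-normal shape, and becomes material from a within-patient CV of about 20%.

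The harm is to the estimate, not to the error rate of the listed tests on levels. The secondary comparison is valid under no effect but gives up roughly 10 points of power, mainly for want of baseline adjustment. It would be wrong to read that loss as the price of the percentage scale or of the normality switch.

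**What to change.** Define the endpoint for NO, cGMP and ET-1 as log(week 4/baseline). Report it within each arm, back-transformed, as a geometric mean percentage change with 95% CI.

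For the comparison with placebo, pre-specify one model for all three markers: log week-4 level on arm and log baseline, giving the avanafil/placebo ratio with 95% CI. Replace the choice of test by normality with this model, and keep the rank tests as sensitivity analyses. A median percentage change with its CI would also deal with the bias in the estimate, but would not recover the efficiency lost without baseline adjustment.

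The cost is SAP wording only; the baseline values are already collected and SPSS can fit the model. There are two small downsides: readers see geometric rather than arithmetic percentage changes, and values below the assay limit need a stated substitution.
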